12.3 Planned safety analyses

The long-term safety of BRV at individualized doses will be evaluated by means of the safety analyses. Summary tables will be presented over the Evaluation Period for all subjects and by categories of total duration of exposure.

All safety variables will be analyzed by descriptive methods on the Safety Population. Treatment-emergent adverse events will be summarized in incidence tables by categories of total duration of exposure and by Medical Dictionary for Regulatory Activities (MedDRA[®]) Primary System Organ Class and Preferred Term. Separate tables will be provided for AEs leading to withdrawal from the study and SAEs.

Laboratory values, vital signs, and weight will be summarized by period and visit. Possibly clinically significant treatment-emergent abnormalities for laboratory values, vital signs, and weight will be listed and summarized by period and visit. Electrocardiogram abnormalities, as well as physical and neurological abnormalities, will also be listed by period and visit.

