12.7 Handling of dropouts or missing data

Safety and efficacy variables will be analyzed as they are available. Days with missing information will be ignored in the calculation of the seizure frequency.

Since subjects will drop out at different times from the study, results will be presented by categories of duration of exposure.

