3.2.7 Exposure duration and exposure duration cohorts

At the final analysis, the overall duration of exposure (or On Treatment Period) will be calculated as the date of last dose of BRV minus the date of first dose of BRV plus 1 day.

Each subject will be classified into one or more of the following exposure duration cohorts based on the duration of BRV exposure as calculated above:

All subjects	≥1 day
≥3 months	≥90 days
≥6 months	≥180 days
≥12 months	≥360 days

This categorization will continue in 6-month increments past 12 months up to a time point that will be determined based on cumulative exposure at the time of the database lock.

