4.2 Handling of dropouts or missing data

Seizure frequency (subjects with POS) and seizure days (subjects with PGS) will be calculated over non missing diary days during each study period or time interval as described in Section 3.2.4 and Section 3.2.5; diary days for which seizure data were not obtained will not be considered in the calculation of seizure frequency or seizure days. Because the evaluation of efficacy is not the primary objective of this study, and because this is an uncontrolled study in a variable setting, which allows individualized optimization of dosing

of BRV and concomitant AEDs, no summaries assessing the impact of missing seizure diary days are planned.

For subjects who prematurely discontinue during the Evaluation Period, the calculation of POS frequency and PGS seizure days will be based on available seizure diary while the subject was receiving BRV. The presence of such dropouts may influence the evaluation of the long-term outcomes for subjects who either do not discontinue or do not discontinue early in the study. Therefore, as described below, selected summaries will be produced by exposure duration cohorts to allow an assessment of long-term outcomes without the potentially confounding influence of earlier discontinuations.

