8.1.1 Partial onset seizure frequency

Twenty-eight day adjusted POS frequency will be summarized with quantitative descriptive statistics for all subjects for the Baseline Period, the On Treatment Period, and by 3-month time intervals over the On Treatment Period. The summary over the On Treatment Period will include all subjects in the POS Efficacy Analysis Set. Similar summaries will be provided for the full cohort interval and by 3-month time intervals for each exposure duration cohort.

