11.2.2 General summaries of TEAEs

Pre-treatment AEs will be provided in a subject data listing; no summaries of pre treatment AEs are planned.

An overall summary of AEs will provide the overall number of TEAEs and the numbers and percentages of subjects with at least 1 TEAE, with a TEAE that led to permanent discontinuation of study drug, with a drug-related TEAE, with a severe TEAE, with a treatment-emergent SAE, and with a drug-related treatment-emergent SAE. The number and percentage of subjects who died will also be summarized. This summary will be provided for all subjects in the Safety Analysis Set and also by subgroup for geographic region and seizure type.

The following summaries of TEAEs will be provided by MedDRA SOC and PT. All summaries are for the combined Evaluation, Down-Titration, and Post-Treatment Periods unless otherwise indicated.

Overall Incidence Summaries

- Incidence of TEAEs
- Incidence of TEAEs by 3-month time interval
- Incidence of TEAEs by study period (Evaluation, Down-Titration, Post-Treatment)
- Incidence of TEAEs for TEAEs occurring in at least 5% of subjects
- Incidence of TEAEs by 3-month time intervals for TEAEs occurring in at least 5% of subjects overall
- Incidence of non-serious TEAEs occurring in at least 5% of subjects

The incidence of TEAEs occurring in at least 5% of subjects will be summarized overall as noted above and also by subgroup for geographic region, seizure type, and randomized treatment from the previous double-blind study.

A subject is included in a 3-month interval if the subject was receiving BRV at any time during that interval based on their duration of exposure to BRV (eg, a subject with exposure for 91 days is included in the time interval for Months 1-3 and Months 4-6). Summaries of AEs by 3-month intervals will include all subjects who are classified into each time interval as defined above. TEAEs which had onset prior to or on the date of the last dose of BRV) are included in summaries by 3-month time intervals.

Maximum Intensity and Causality

- Incidence of TEAEs by maximum intensity
- Incidence of drug-related TEAEs

Serious Adverse Events

- Incidence of treatment-emergent SAEs

Discontinuations due to TEAE

- Incidence of TEAEs leading to permanent discontinuation of study drug

TEAEs of interest

AEs of interest will be identified based on MedDRA search criteria, which are documented outside of the SAP. The following summaries will be provided for AEs of interest:

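### SAP 11.2.2 omits the TEAE tables by duration of exposure that Protocol 12.3 specifies, so an apparent change in AE incidence across 3-month intervals cannot be separated from selective dropout

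*SAP*

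**What the plan says.** **Protocol.** Section 12.3 sets the layout of the safety tables: "Summary tables will be presented over the Evaluation Period for all subjects and by categories of total duration of exposure". It then names the AE tables: "Treatment-emergent adverse events will be summarized in incidence tables by categories of total duration of exposure", with SOC and PT as the further breakdown. Section 12.7, which covers safety and efficacy variables together, gives the reason: "Since subjects will drop out at different times from the study, results will be presented by categories of duration of exposure".

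**SAP, construction of the cohorts.** Section 3.2.7 provides the tool: "Each subject will be classified into one or more of the following exposure duration cohorts". The cohorts are nested: all subjects, at least 3, 6 and 12 months, then 6-month steps. Section 4.2 says what they are for: "selected summaries will be produced by exposure duration cohorts to allow an assessment of long-term outcomes without the potentially confounding influence of earlier discontinuations".

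**SAP, use of the cohorts.** Section 8.1.1 applies them to seizure frequency: "Similar summaries will be provided for the full cohort interval and by 3-month time intervals for each exposure duration cohort". Sections 8.1.2, 8.1.3 and 8.2 do likewise for percent reduction, responders, seizure freedom and the generalized-seizure outcomes. Section 11.1 applies them to exposure and modal dose.

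**SAP, TEAEs.** Section 11.2.2 plans TEAEs overall, by 3-month interval, by study period, at a 5% threshold, by subgroup, by intensity and by causality. It also plans SAEs, TEAEs leading to discontinuation and AEs of interest. None is by exposure duration cohort. A subject enters a 3-month column after any time on brivaracetam in that interval, and "Summaries of AEs by 3-month intervals will include all subjects who are classified into each time interval as defined above".

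**The concern.** There are two linked problems.

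First, a table that the protocol names is missing from the SAP with no reason given. Elsewhere the SAP does explain itself when it departs from the protocol, for example on pharmacoeconomic summaries (2.2.2.3) and study drug compliance (section 7).

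Second, the tables that do show AEs along the time axis have a changing membership. Months 1-3 describe nearly everyone and Months 22-24 describe those who stayed. Withdrawal due to AE is itself a primary safety variable, so a link between AE risk and leaving is plausible. A falling series could then be read as improving tolerability with continued treatment when it only reflects who left. Long-term safety and tolerability is the primary objective and TEAE occurrence a primary safety variable, so this is a reading that a study report could easily invite.

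**Working it through.** **1. Is the table really absent?** Setting the sections side by side:

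| Output | Planned by exposure duration cohort? |
|---|---|
| Seizure frequency/days, percent reduction, responders (SAP 8.1, 8.2.2) | Yes, over the cohort interval and by 3-month interval |
| Seizure freedom (8.2.1.1, 8.2.2.4) | Yes |
| Exposure and modal dose (11.1) | Yes |
| QOLIE-31-P, HADS (8.2.3, 11.4.5) | No; study visit cohorts are used |
| TEAEs (11.2.2) | No |

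A 3-month interval is a time window, while total duration of exposure is a fixed attribute of the subject. The 3-month tables therefore do not stand in for the protocol's table. The record of Protocol Amendment 2 shows that the sponsor treats these as different things: the replaced text of the safety section listed time windows, periods and exposure categories separately.

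**2. Can attrition alone produce a decline?** The plan has no figure to reproduce. It is descriptive and has no sample size calculation. Every rate below is an assumption.

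Take two classes of subject, each with constant risk:
- AE-prone, 25% of subjects: TEAE rate 0.6 per quarter, so quarterly incidence is 1 − e^(−0.6) = 45.1%.
- Others, 75%: rate 0.15, so 1 − e^(−0.15) = 13.9%.
- Discontinuation rate per quarter: d in the AE-prone (0.25 or 0.12) and 0.04 in the others.

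Counting subjects who complete quarter k, the AE-prone share is

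s(k) = 0.25·e^(−dk) / [0.25·e^(−dk) + 0.75·e^(−0.04k)]

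and the incidence is 13.9% + s(k) × 31.2 points.

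| d | s(1) | Incidence, quarter 1 | s(8) | Incidence, quarter 8 | Fall |
|---|---|---|---|---|---|
| 0.25 | 0.213 | 20.6% | 0.058 | 15.8% | 4.8 points |
| 0.12 | 0.235 | 21.3% | 0.149 | 18.6% | 2.7 points |
| 0.04 (equal) | 0.250 | 21.7% | 0.250 | 21.7% | 0 |

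In the fixed cohort treated for at least 24 months the share is s(8) in every quarter, so incidence is flat at 15.8% or 18.6%.

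**3. Against sampling noise.** Assume 700 entrants, within the 650 to 720 expected from N01358, and treat the two quarters as independent.
- d = 0.12: 700 × (0.0957 + 0.5446) = 448 complete quarter 8. SE = √(0.186 × 0.814 / 448) = 1.8 points. In quarter 1, n = 660 and SE = 1.6. SE of the difference = √(1.6² + 1.8²) = 2.4, so the fall is about 1.1 SE.
- d = 0.25: 405 remain, the SE of the difference is again 2.4 points, and the fall is about 2.0 SE.

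**4. Under the SAP's own inclusion rule.** Step 2 counts complete quarters only. A simulation of 400,000 subjects over eight 90-day intervals used the SAP rule, under which any time on drug in an interval counts. Risk was again constant, with 30% AE-prone at 70% risk per 90 days against 30% in the rest:

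| Dropout per 90 days, prone / rest | Months 1-3 | Months 10-12 | Months 22-24 | Cohort ≥12 months, first four intervals |
|---|---|---|---|---|
| 10% / 10% | 40.1% | 40.3% | 40.3% | 41.9-42.1% |
| 15% / 5% | 40.2% | 38.0% | 35.3% | 38.6-38.8% |
| 25% / 5% | 39.3% | 35.1% | 32.0% | 35.5-35.8% |
| 35% / 3% | 38.4% | 32.9% | 30.5% | 33.1-33.4% |

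A milder contrast (50% prone, risks 60% and 40%, dropout 15% and 5%) falls from 47.6% to 44.5%. Dividing by exposure time does not help: in the 25% / 5% case the rate falls from 59.1 to 41.5 events per 100 subject-intervals.

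**The case against.** **The harm does not follow from the missing protocol table.** This stands. Protocol 12.3 asks for incidence by exposure category, not by interval within category. Nested cohorts compared with one another mix longer observation with selection for staying, so that table shows no clean time trend. Restoring it brings the SAP back to the protocol. Only the within-cohort interval table addresses the trend, and that goes beyond the protocol text.

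**Nothing is lost from the primary variables.** This also stands. TEAEs, SAEs and TEAEs leading to discontinuation are tabulated for the whole Safety Population, early leavers included. Kaplan-Meier retention to 60 months and reasons for discontinuation make attrition visible.

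**The size is assumed.** True. Protocol 2.4 and 5.4 describe discontinuation due to TEAEs as low in earlier studies, and entrants have already completed a prior study. All the declining scenarios assume at least three-fold differences in dropout.

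**SAP 4.2 promises only selected summaries.** That wording does not give a reason for leaving out a table that the protocol names.

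Three stronger readings are tempting and should not be made:
- *That the protocol also specifies SAE tables by exposure category.* The current SAE sentence in 12.3 does not say so, and Amendment 2 took the phrase out of it. Only the general opening sentence of 12.3 could cover SAEs.
- *That the 3-month TEAE table is the only planned view of safety over time.* TEAEs by study period, AEs of interest by interval, laboratory values and vital signs by visit, and HADS by visit cohort are also planned.
- *That the silence of the SAP's amendment section shows a concealed change.* That section lists changes between SAP versions. It is not a register of departures from the protocol.

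**Conclusion.** The mismatch between Protocol 12.3/12.7 and SAP 11.2.2 is plain in the text and should be corrected or justified. The consequence is a risk of misreading, not a demonstrated bias. The 3-month TEAE tables can decline through attrition alone, provided that subjects at higher AE risk discontinue sooner. Under the rates in step 2 the artificial decline is 2.7 to 4.8 points over 24 months, or about 1 to 2 standard errors of the first-to-last difference. The other assumed rates, under the SAP's inclusion rule, give 0 to 8 points. The documents cannot narrow this range, and it is zero if dropout is unrelated to AE risk. No planned statement that AE incidence falls with time appears in either document, so the point concerns how the tables may be read. It is a should-fix.

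**What to change.** In SAP 11.2.2, for the Safety Population:

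1. Add incidence of TEAEs by SOC and PT for each exposure duration cohort of SAP 3.2.7, as Protocol 12.3 specifies. If the table is not wanted, state the departure and the reason.
2. As an improvement beyond the protocol text, add incidence of TEAEs by 3-month interval within each cohort over the cohort interval, on the pattern of SAP 8.1.1 to 8.1.3. State that any comment on change in AE incidence over time will rest on this table and not on the all-subjects interval table.

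Cohort tables for SAEs are optional. The cohorts should not be used for TEAEs leading to discontinuation, because cohort membership excludes earlier stoppers by construction.

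The cost is SAP wording and extra tables from cohorts already derived, with no new data. Output becomes longer, and each cohort table needs a note that its members are selected for having stayed on brivaracetam, so its level of incidence does not describe all treated subjects.

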4 STUDY VARIABLES

4.1 Safety variables

4.1.1 Primary safety variables

- Occurrence of a TEAE
- Withdrawal due to AE
- Occurrence of an SAE

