5.1.3 Anticipated regions and countries

The regions and countries for enrollment will be the same as in the previous studies, N01358 and N01258. N01358 is planned to be performed in North America (Canada and USA), Western Europe, Latin America, Eastern Europe, Asia, and Africa, and N01258 is planned to be performed in the USA and Europe, with possible extension to other countries or regions for both studies.

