4.8 Examination of subgroups

Selected summaries will be provided for the following subgroups as specified within each of the following sections:

- Two mappings of countries to regions are defined, 1 based on the classification requested by Food and Drug Administration (FDA), and 1 based on the regional classification for the CHMP (Committee for Medicinal Products for Human Use).

Countries will be mapped to geographic regions as follows for the FDA:

Geographic Region (FDA)	Country
North America	Canada, United States, Puerto Rico
Latin America	Brazil, Mexico
Western Europe	Austria, Belgium, Finland, France, Germany, Ireland, Italy, Netherlands, Norway, Réunion, Spain, Sweden, United Kingdom, Switzerland
Eastern Europe	Bulgaria, Czech Republic, Estonia, Latvia, Hungary, Lithuania, Poland, Romania, Russia, Serbia and Montenegro, Turkey, Ukraine
Asia/Pacific/Other	Australia, Hong Kong, India, Israel, Japan, Singapore, South Africa, Republic of Korea, Taiwan, Tunisia

Countries will be mapped to geographic regions as follows for the CHMP:

Geographic Region (CHMP)	Country
North America	Canada, United States, Puerto Rico
Latin America	Brazil, Mexico
Europe (European Union [EU] member states) *	Austria, Belgium, Bulgaria, Czech Republic, Estonia, Finland, France, Germany, Hungary, Ireland, Italy, Latvia, Lithuania, Netherlands, Norway, Poland, Réunion, Romania, Spain, Sweden, United Kingdom
Europe (non-EU member states)	Russia, Serbia and Montenegro, Switzerland, Turkey, Ukraine
Asia/Pacific/Other	Australia, Hong Kong, India, Israel, Japan, Singapore, South Africa, Republic of Korea, Taiwan, Tunisia

* EU member states plus Norway.

- Seizure type (Partial Onset Seizures, Primary Generalized Seizures)
- Randomized treatment in the previous study (placebo [PBO], BRV) (TEAEs only)

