11.1 Extent of exposure

A daily dose will be calculated for each study day from the day of first dose of BRV to the day of last dose of BRV for the purposes of calculating modal dose. Daily dose will be calculated as the sum of the AM and PM dose for each day.

Modal daily doses will be calculated across all study days on or after the day of first dose of BRV and up to and including the day of last dose of BRV. Modal daily dose is the most frequently taken daily dose during this period. In the event of a tie, the modal dose will be set to the lower of the tied doses. Modal daily dose will be categorized as follows:

Category	Definition
5 mg/day	<20mg/day
20mg/day	≥20mg/day to <50mg/day
50mg/day	≥50mg/day to <100mg/day
100mg/day	≥100mg/day to <150mg/day
150mg/day	≥150mg/day to <200mg/day
200mg/day	≥200mg/day

Subject years of exposure will be calculated by summing the exposure duration in days for all subjects being summarized, and dividing the resulting value by 365.25.

Subject years of exposure will be presented overall and by modal dose for the Safety Analysis Set. The subject years of exposure presented by modal dose will be the total subject years of exposure of subjects with that modal dose.

The number and percentage of subjects exposed to BRV will be summarized overall and by modal dose category. The number and percentage of subjects in each Exposure Duration Cohort (≥3 months, ≥6 months, ≥12 months, and so forth) will be summarized.

The number and percentage of subjects within each modal dose category will be summarized for each Exposure Duration Cohort; percentages will be relative to the total number of subjects in each Exposure Duration Cohort.

In addition to the overall summaries of the above, the above will also be summarized by subgroup for region (North America, Europe [EU member states], Europe [non-EU member states], Asia/Pacific/Other), and seizure type (Partial Onset Seizures, Primary Generalized Seizures).

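### SAP 11.2.2 summarises treatment-emergent SAEs and TEAEs leading to discontinuation only as whole-study percentages, with no time horizon or person-time rate; separately, the SAP 11.1 exposure list omits Latin America

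*SAP*

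**What the plan says.** Protocol 4.1.1 names three primary safety variables: occurrence of a TEAE, "Withdrawal due to AE", and occurrence of an SAE. SAP 2.2.1.1 repeats them.

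SAP 11.2.2 covers the last two in two places.

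- **Overall AE table.** It gives numbers and percentages of subjects. Of this table the SAP says: "This summary will be provided for all subjects in the Safety Analysis Set and also by subgroup for geographic region and seizure type".
- **SOC/PT tables.** There is one for each outcome: "Incidence of treatment-emergent SAEs" and "Incidence of TEAEs leading to permanent discontinuation of study drug". The default window is the Evaluation, Down-Titration and Post-Treatment Periods combined unless the SAP says otherwise. It does not say otherwise for these two.

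The same section plans 3-month tables for all TEAEs, for TEAEs in at least 5% of subjects and for TEAEs of interest. The inclusion rule is: "A subject is included in a 3-month interval if the subject was receiving BRV at any time during that interval".

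SAP 11.1 plans subject-years of exposure overall, by modal dose, and by "region (North America, Europe [EU member states], Europe [non-EU member states], Asia/Pacific/Other), and seizure type". SAP 4.8 defines two country-to-region mappings, one for FDA and one for CHMP. Each has five regions, and each includes Latin America (Brazil, Mexico). Protocol 5.1.3 says: "N01358 is planned to be performed in North America (Canada and USA), Western Europe, Latin America, Eastern Europe, Asia, and Africa".

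**The concern.** Follow-up per subject is open-ended. Protocol 5.1.1 puts the start of recruitment at about Q2 2011, and the SAP amendment was approved on 4 February 2019. Exposure can therefore run from one day to several years. The share of subjects who ever had an SAE, or ever stopped because of a TEAE, then mixes how often the event occurs with how long subjects stayed. Two regions or seizure-type groups with the same event rate can show different percentages only because one group stayed longer.

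The primary objective is long-term safety, and a reader will want to know whether these events come early or keep accruing. As planned, the summary tables cannot show that for the two most consequential AE outcomes, although they can for TEAEs in general.

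The region list is a separate and smaller matter. As written, Latin American subjects have no row in the exposure-by-region table, and the regions used for events may not be those used for exposure.

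**Working it through.** The plan states no event rate, sample size calculation or alpha, so there is no figure to reproduce. The first two steps are textual. The rates in steps 3 to 5 are assumptions.

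**1. Does any planned output give these two outcomes a time axis?**

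| Place in SAP | What it gives | Fills the gap? |
|---|---|---|
| 3.2.5 | General statement that 3-month intervals serve AE analysis | No: 11.2.2 assigns interval tables output by output and assigns none to these two |
| 11.2.2, all-TEAE 3-month table | All TEAEs by interval | No: serious or treatment-ending events are not identifiable in it |
| 5.1, disposition | Count of discontinuations by reason | No: no time point |
| 5.1, Kaplan-Meier | Retention at 3 to 60 months | No: any permanent discontinuation is an event, whatever the cause |
| 11.1, subject-years | Exposure totals | Partly: not used as a denominator in 11.2.2 (see step 4) |
| 3.1 and 3.2.2 | Listings and relative day | Only by rebuilding from individual data |

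Tables with an interval, exposure cohort or person-time denominator for either outcome: none.

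**2. Regions.** The CHMP mapping in 4.8 has North America, Latin America, EU, non-EU Europe and Asia/Pacific/Other. The 11.1 list has four of these, and the one missing is Latin America. SAP 11.2.2 refers to geographic region without naming a mapping.

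**3. How a crude percentage moves with follow-up.** Take a constant first-event hazard l, other dropout d and horizon T:

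crude = l/(l+d) × (1 − exp(−(l+d)T)).

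With l = 0.05 and d = 0.20 per year, crude is 4.4% (T = 1), 7.9% (T = 2), 14.3% (T = 5) and 16.5% (T = 7). The underlying rate is 5.0 per 100 subject-years at risk throughout.

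For two subgroups with the same l = 0.10 and T = 5, where one has d = 0.1:

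| d in the other group | Crude, d = 0.1 | Crude, other group | Ratio |
|---|---|---|---|
| 0.1 | 31.6% | 31.6% | 1.00 |
| 0.2 | 31.6% | 25.9% | 1.22 |
| 0.3 | 31.6% | 21.6% | 1.46 |
| 0.4 | 31.6% | 18.4% | 1.72 |

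The distortion follows the assumed dropout difference and vanishes without one. It depends less on l: for d = 0.1 versus 0.4 the ratio is 1.80, 1.77, 1.72 and 1.64 at l = 0.02, 0.05, 0.10 and 0.20.

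**4. What a reader could do with the planned subject-years** (l = 0.10, T = 5).

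- SAEs: drug continues after the event, so total exposure per subject is (1 − exp(−dT))/d, which is 3.935 years (d = 0.1) or 2.162 years (d = 0.4). Then 0.3161/3.935 = 8.0 and 0.1836/2.162 = 8.5 per 100 subject-years. The ratio is 1.06, but both fall below the true 10.0.
- Discontinuations: drug stops after a lag g, and the ratio is 1/(1/l + g). That gives 9.9 with g = 28 days and 9.8 with g = 56 days, the same in both groups.

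**5. Limits of a single rate.** Under a constant hazard, crude divided by time at risk equals l by construction, so agreement between groups there proves nothing. Suppose instead that the hazard is 0.10 in year 1 and 0.02 in years 2 to 5. Time at risk is A1 = (1 − exp(−(0.10+d)))/(0.10+d) in year 1, and A2 = exp(−(0.10+d)) × (1 − exp(−4(0.02+d)))/(0.02+d) afterwards. The rate is (0.10·A1 + 0.02·A2)/(A1 + A2).

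- d = 0.1: A1 = 0.906, A2 = 2.601, rate 4.1 per 100 subject-years.
- d = 0.4: A1 = 0.787, A2 = 1.175, rate 5.2 per 100 subject-years.

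So a rate alone can still depend on follow-up, and interval rows are needed beside it.

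**The case against.** - **The choice looks deliberate.** The log of Protocol Amendment 2 shows that an exposure-duration split for exactly these two tables was removed. The current sentence in Protocol 12.3 promises only separate tables, and SAP 11.2.2 provides them. This stands. A reader might infer that the SAP departs from the protocol on these two outcomes, but the current sentence about them does not support that.
- **A percentage matches the variable as defined.** The variables are occurrences, the study has one arm, and SAP 3.1 plans no testing. This stands too, but it does not make a percentage with no time horizon interpretable under open-ended follow-up.
- **Planned subject-years narrow the gap.** Step 4 confirms this: the approximation is close for discontinuations, and for SAEs it mostly removes the subgroup contrast, though it understates the rate. The reader must still do the division.
- **The 1.72 ratio is constructed.** It needs a fourfold dropout difference that no document supports. A reader might infer that the planned subgroup tables are distorted by about that much; nothing in the documents shows it.
- **Latin America may be a drafting slip.** That is likely. A reader might infer that these subjects leave the safety analysis. They do not: they remain in the Safety Population and in the overall figures. If the four listed rows follow the CHMP mapping, their exposure is the overall total minus those rows. The number enrolled there is not given.

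**Conclusion.** The concern holds as a weakness of interpretation. Treatment-emergent SAEs and TEAEs leading to discontinuation have no time-based summary, while less consequential TEAE groupings do. No test and no sample size is affected.

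The size cannot be stated from the documents, which give neither event nor dropout rates. Under the assumed rates in step 3, the same underlying rate reads anywhere from 4.4% to 16.5% depending only on follow-up of 1 to 7 years. Subgroup percentages are distorted only as far as exposure differs between subgroups; the illustrated ratios run from 1.00 to 1.72.

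The region inconsistency is certain on the text and editorial in nature.

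A minor related point concerns TEAEs overall. Protocol 12.3 plans incidence tables by category of total exposure, and Protocol 12.7 gives differing dropout times as the reason for such categories. SAP 11.2.2 lists none. Its 3-month tables largely serve that purpose, but the SAP does not say that they replace the exposure-category tables.

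**What to change.** 1. **Rates (SAP 11.2.2).** For both outcomes, overall and by region and seizure type, add subjects with a first on-treatment event per 100 subject-years at risk, counting time from first dose to first event or last dose. Label the rate as on-treatment and show its matching count, because the existing percentages also include post-treatment events and the two will not agree.
2. **Intervals (SAP 11.2.2).** Add one any-event row per 3-month interval for each outcome, under the inclusion rule already in that section and without SOC/PT rows. Pool sparse late intervals by a rule stated in advance.
3. **Regions.** Add Latin America to the SAP 11.1 list, name one SAP 4.8 mapping, and use it for both events and exposure.
4. **Minor.** For TEAEs overall, add the exposure-category table of Protocol 12.3 or state that the 3-month tables replace it.

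The cost is SAP wording and a few tables from AE onset, first-dose and last-dose dates; no new data are needed.

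The downside is sparse late intervals. From 1 April or 30 June 2011 to 4 February 2019 is 2,866 or 2,776 days, so at most 31 to 32 intervals of 90 days by SAP approval. Assume 650 to 820 subjects (720 + 100 at the top), an SAE hazard l of 0.05 to 0.10 and dropout of 0.2 per year. Subjects with an SAE in the interval starting at year t are N·exp(−0.2t) × l/(l+0.2) × (1 − exp(−(l+0.2)·90/365.25)). That gives about 8 to 20 in the first interval and 3 to 7 in the one starting at year 5.
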